- time to first acute exacerbation of CRS, defined as a worsening of symptoms that requires escalation of treatment
- percent of subjects requiring rescue medication after Week 4
- change from baseline to Week 24/ET in the 36-Item Short Form Health Survey version 2 (SF36v2) mental component score (MCS)
- change from baseline to Week 24/ET in the SF36v2 physical component score (PCS)
- change in patient-reported outcomes from baseline to Week 24/ET as measured by:
  - change in sleep quality from baseline to Weeks 12 and 24/ET, using the PSQI
  - percent of subjects improved as indicated in the Patient Global Impact of Change (PGIC) at Week 4 and Week 24/ET
  - SF-36v2, 8 individual, physically and emotionally based domains (physical functioning, role-physical, bodily pain, general health, vitality, social functioning, role-emotional, and mental health) standardized scores
  - change in the severity of depression from baseline to Week 24/ET and severity of depression at Week 24/ET as measured by the Quick Inventory of Depression Symptomatology (QIDS)
  - change in severity of olfactory symptoms from baseline to Week 24/ET as measured by the Smell Identification Test (SIT)
  - EuroQol-5 (EQ-5D)

- Short Form-6 dimension (SF-6D) derived scores from the SF-36v2
- assessment of health economic measures during the double-blind treatment phase related to CRS (eg, criteria for surgical intervention for CRS is met [independent of actual surgery performed], subjects who entered the study approved for surgery [with a scheduled surgery date] who no longer elect to undergo surgery, missed work or school days/lost productivity) by Health and Work Performance Questionnaire (HPQ)

The following secondary objectives will compare the efficacy of twice daily doses of 186 and 372 µg of OPN-375 with placebo by pooling the data from Study OPN-FLU-CS-3205 with Study OPN-FLU-CS-3206, which is a separate study being conducted in parallel to this study. It has identical study objectives and study design but only includes subjects with CRS without nasal polyps:

- change from baseline to Week 24/ET in subject symptoms and functioning, as measured by Sinonasal Outcome Test-22 (SNOT-22) total score in subjects who report using an intranasal, topically acting nasal steroid for the treatment of CRS within 30 days of Visit 1
- change in sleep quality from baseline to Week 24/ET, using the Global Pittsburgh Sleep Quality Index (PSQI) Score

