## **2.5 Number of Subjects and Duration of Study**

The total planned number of subjects is approximately 333. Approximately 333 subjects will be randomly assigned to receive 1 of the 2 active treatments or placebo (111 subjects in each group); subjects will be randomized using a 1:1:1 ratio.

The expected participation period for a subject is approximately 26 weeks, including a pretreatment phase consisting of a Screening visit followed by a 7- to up to 21-day single-blind placebo run-in period and a 24-week double-blind treatment phase.

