#### **4.2 Exclusion Criteria**

Potential subjects who meet any of the following criteria will be excluded from entering this study:

1. women who are pregnant or lactating
2. inability to have each nasal cavity examined for any reason, including nasal septum deviation
3. inability to achieve bilateral nasal airflow
4. is currently taking XHANCE
5. have previously used XHANCE for more than 1 month and did not achieve an adequate symptomatic response
6. the nasal/sinus anatomy prevents the accurate assessment of sinus volume via CT scan
7. history of sinus or nasal surgery within 6 months before Visit 1 or has not healed from a prior sinus or nasal surgery
8. have current evidence of odontogenic sinusitis, sinus mucocele (the affected sinus is completely opacified and either the margins are expanded and/or thinned OR there are areas of complete bone resorption resulting in bony defect and extension of the “mass” into adjacent tissues), evidence of allergic fungal sinusitis, or evidence of complicated sinus disease (including, but not limited to, extension of inflammation outside of the sinuses and nasal cavity)
9. have a paranasal sinus or nasal tumor
10. have a polyp extending outside the OMC/middle turbinate (anterior or inferior) that is below the inferior turbinate attachment as determined by the nasoendoscopy at screening

11. have a nasal septum perforation
12. have had more than 1 episode of epistaxis with frank bleeding in the month before Visit 1 (Screening)
13. have evidence of significant mucosal injury, ulceration (eg, exposed cartilage) on Visit 1 (Screening) nasal examination/nasoendoscopy
14. have current, ongoing rhinitis medicamentosa (rebound rhinitis)
15. have significant oral structural abnormalities (eg, a cleft palate)
16. have a diagnosis of cystic fibrosis
17. history of eosinophilic granulomatosis with polyangiitis (Churg–Strauss syndrome) or dyskinetic ciliary syndromes
18. Symptom resolution or last dose of antibiotics for purulent nasal infection, acute sinusitis, or upper respiratory tract infection, influenza, or SARS-CoV-2 (COVID-19) has not occurred before Visit 1 or was less than 4 weeks before the CT scan. Potential subjects presenting with any of these infections may be rescreened 4 weeks after symptom resolution.
19. planned sinonasal surgery during the period of the study
20. allergy, hypersensitivity, or contraindication to corticosteroids or steroids

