### 7.3 Health Economic Assessments

Health economic information related to bilateral CRS will be collected during the study and will include information on criteria for surgical intervention (independent of actual surgery performed), subjects approved for surgery, who no longer elect to undergo surgery, and missed work or school days/lost productivity. The investigator will ask the subject if he/she would consider surgery and the subject will complete the HPQ (1-2 minutes to complete).

Objective criteria for surgical intervention are as follows:

- those with polyps present who have:
  - used a topical intranasal corticosteroid ( $\geq 8$  weeks duration)
  - used a short-course of systemic corticosteroid (1- to 3-week duration)

- SNOT-22 total score  $\geq 20$
- Lund-Mackay CT score  $\geq 1$
- those without polyps present who have:
  - used topical intranasal corticosteroid ( $\geq 8$  weeks duration)
  - used either a short course of broad-spectrum/culture-directed systemic antibiotic (2 to 3 weeks duration) or a prolonged course of systemic low-dose anti-inflammatory antibiotic (ie, macrolide or trimethoprim/sulfamethoxazole) ( $\geq 12$  weeks duration)
  - SNOT-22 total score  $\geq 20$
  - Lund-Mackay CT score  $\geq 1$
- subjects who enter the study approved for surgery with a scheduled surgery date, who no longer elect to undergo surgery
- The work productivity questionnaire asks about employment status, work absences, and on-the-job productivity. Subjects will also be asked to provide annual salary and postal code information at screening which will be used to inform overall cost to employers from lost work productivity.

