- Zinreich modification of the Lund-Mackay Staging System total score, scores for ethmoids and maxillary sinuses combined, and for each sinus pair (e.g., ethmoids, maxillary, frontal, and sphenoid)
- Zinreich modification of the Lund-Mackay Staging System score for the worst sinus between maxillary and ethmoid sinuses
- SF36v2 MCS Domain, PCS Domain, and individual health domains
- QIDS total score
- SIT scores

Change from baseline to Week 24/ET for EQ-5D VAS scores will be analyzed with the ANCOVA model described above; EQ-5D dimensions will be summarized. Further details will be provided in the SAP.

The percent of subjects considered improved (ie, subjects with ratings of 1 [very much improved] or 2 [much improved]) based on the PGIC at weeks 4 and 24/ET will be analyzed with a logistic regression MMRM model; further details will be provided in the SAP.

The Kaplan-Meier method and log-rank test will be used to estimate and compare the distributions of time to first exacerbation between OPN-375 and placebo.

The following endpoints will be analyzed using a logistic regression model; further details will be provided in the SAP:

- QIDS Severity of Depression at Week 24/ET
- The percent of subjects requiring rescue medication from Week 4 to Week 12; subjects without use of any rescue medication during the period Week 4 to Week 12 will be referred to as rescue-free subjects.
- The percentage of subjects who meet the eligibility criteria for surgery at Week 24

The percent of subjects indicating that they are willing to consider sinus surgery at baseline and Week 24, and the percent of subjects approved for surgery who no longer elect to undergo a surgery Week 24 within each treatment group will be compared with McNemar's test.

The total number of times a subject requires rescue medication after Week 4 to Week 12 will be tabulated. Rescue free subjects will be assigned a zero ('0') for this tabulation. This endpoint will be analyzed with an ANCOVA model based on ranks.

Change from baseline to Week 24/ET for SF-6D will be summarized as described in the SAP.

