3.4.5 HEOR Endpoints and Assessments

Health economic information related to chronic rhinosinusitis will be collected during the study and will include information on criteria for eligibility for escalation of care to surgical intervention (independent of actual surgery performed) for subjects approved for surgery, who no longer elect to undergo surgery, and missed work or school days/lost productivity. The investigator will ask the subject if he/she would consider surgery and the subject will complete the Health Productivity Questionnaire (HPQ).

Objective criteria for being eligible for surgical intervention are listed below for subgroups of subjects with and without polyps.

Subjects **with polyps** present at baseline who meet the following criteria:

- used a topical intranasal corticosteroid (≥ 8 weeks duration)
- used a course of systemic corticosteroid (1- to 3-week duration)
- SNOT-22 total score ≥ 20
- Lund-Mackay CT score ≥ 1

Subjects **without polyps** present at baseline who have:

- used topical intranasal corticosteroid (≥ 8 weeks duration)
- used either a short course of broad-spectrum/culture-directed systemic antibiotic (2 to 3 weeks duration) or a prolonged course of systemic low-dose anti-inflammatory antibiotic (i.e., macrolide or trimethoprim/sulfamethoxazole) (≥ 12 weeks duration)
- SNOT-22 total score ≥ 20
- Lund-Mackay CT score ≥ 1

The World Health Organization (WHO) Health and Performance Questionnaire (HPQ) is a work productivity questionnaire which asks about employment status, work absences, and on-the-job productivity. Based on HPQ work productivity questions, a comparison of health economic measures during the double-blind treatment phase related to CRS will include:

- percent of subjects indicating that they are willing to consider sinus surgery at baseline and Week 24/ET

- percent of subjects who meet the minimal objective criteria for surgical intervention (as defined in Section 7.6.1) at baseline and Week 24/ET
- percent of subjects approved for surgery who no longer elect to undergo a surgery Week 24/ET
- number and percentage of missed work days and the percentage of productive hours lost while at work from the HPQ

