7.6 Health Economic Outcomes Research (HEOR) Endpoints

7.6.1 Surgical Intervention Assessment (SIA)

The surgical intervention assessment (SIA) is performed at baseline and Week 24/ET. This assessment includes a question to the subject as well as an objective assessment.

For the question, subjects are asked, "If symptoms of CRS were to continue at the current severity level would subject consider undergoing sinus surgery if it were recommended to subject today by subject's physician?"

The Surgical Intervention Assessment (SIA) is based on the following pre-defined, objective criteria used to create a standardized determination of whether or not a subject is eligible for sinus surgery.

a) Subjects **with** polyps present at baseline will have to have all of the following:

- used a topical intranasal corticosteroid (≥ 8 weeks duration)
- used a short-course of systemic corticosteroid (1- to 3-week duration)
- SNOT-22 total score ≥ 20
- Lund-Mackay CT score ≥ 1

b) Subjects **without** polyps present at baseline will have to have all of the following:

- used topical intranasal corticosteroid (≥ 8 weeks duration)
- used either a short course of broad-spectrum/culture-directed systemic antibiotic (2 to 3 weeks duration) or a prolonged course of systemic low-dose anti-inflammatory antibiotic (i.e., macrolide or trimethoprim/sulfamethoxazole) (≥ 12 weeks duration)
- SNOT-22 total score ≥ 20
- Lund-Mackay CT score ≥ 1

A subject who satisfies the criteria in either (a) or (b) above is defined to have the event: eligible for sinus surgery. Only subjects who have SIA completed at both baseline and Week 24/ET will be included in the analysis.

The number and percentage of subjects answering Yes/No to the surgery question, and the number and percentage of subjects who are eligible for surgery (Yes/No) based on SIA within each active treatment group and placebo will be summarized in a '2x2' contingency table representing baseline versus Week 24/ET. McNemar's test will be used to assess the extent to which subjects improve ('Yes' at baseline to 'No' at Week 24/ET) versus worsen ('No' at baseline versus 'Yes' at Week 24/ET) within each treatment group, and the odds ratio (improved versus worsened) and 95% confidence interval will be presented for each treatment group.

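### Protocol 9.6 applies a within-arm McNemar test to an approved-for-surgery endpoint in which change can go only one way, its denominator is left undefined beside exclusion 19, and the SAP gives the endpoint no analysis

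*Protocol*

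**What the plan says.** - **Objective.** Protocol 2.3 sets out to compare each dose with placebo. Among the health-economic measures it names "subjects who entered the study approved for surgery [with a scheduled surgery date] who no longer elect to undergo surgery".
- **Assessment.** Protocol 7.3 describes the same group: "subjects who enter the study approved for surgery with a scheduled surgery date, who no longer elect to undergo surgery".
- **Endpoint.** Protocol 3.2.1.3 lists the percentage of approved subjects who no longer choose surgery at Week 24/ET. SAP 3.4.5 keeps it: "percent of subjects approved for surgery who no longer elect to undergo a surgery Week 24/ET". SAP 3.3.3 keeps the objective.
- **Test.** Protocol 9.6 handles this endpoint in the same sentence as the willingness-to-consider-surgery item. It ends: "no longer elect to undergo a surgery Week 24 within each treatment group will be compared with McNemar's test".
- **Eligibility.** Exclusion 19 (Protocol 4.2 and Synopsis) removes anyone with "planned sinonasal surgery during the period of the study". Protocol 2.5 says: "The expected participation period for a subject is approximately 26 weeks".
- **SAP analysis.** SAP 7.6.1 analyses two items, the yes/no surgery question and objective eligibility for surgery. For these, "McNemar's test will be used to assess the extent to which subjects improve" or worsen within each arm, and logistic regression compares the arms at Week 24/ET. It gives nothing for the approved-for-surgery endpoint.
- **Record of changes.** SAP Section 2 says the SAP does not deviate from Amendment 6.0. SAP Section 11 records that the rescue-medication endpoint was removed and is silent on this one.

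**The concern.** There are three separate problems with one endpoint.

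First, the test named in Protocol 9.6 does not suit it. McNemar's test asks whether movement from yes to no is as frequent as movement from no to yes. If everyone counted is a yes at entry, the second kind of movement cannot occur. The test then detects only that some people changed their minds, which can happen under placebo as well as under drug. It is run within each arm, so it does not address an objective framed as a comparison with placebo.

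Second, the denominator is not pinned down. The objective needs subjects who arrive with a surgery date, while exclusion 19 turns away those whose date falls within the study. The overlap is real but narrower than the endpoint wording suggests, and neither document describes it.

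Third, the SAP lists the endpoint without saying how, or on whom, it will be reported. A statement about surgery avoided could end up resting on a within-arm p-value or on an analysis chosen after unblinding.

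**Working it through.** **Plan's own figures.** Neither document gives a sample size, expected count or power for this endpoint. The only stated design figure is 88% power for the co-primary endpoints with 111 per group. It reproduces (0.880 for a CSNS difference of 0.8 with SD 1.9; 0.877 for an APOV difference of 11.3 with SD 27) but has no bearing here.

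**The paired table.** Take the endpoint's denominator as Protocol 2.3 and 7.3 define it, subjects approved with a date at entry. Let b be the number who move from yes to no and c the number who move from no to yes. Nobody starts at no, so c = 0 whatever the treatment. The null of equal movement then holds only if nobody changes. The paired odds ratio b/c is undefined.

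**p-values with c = 0.** Protocol 9.6 does not say which form of the test is meant, so three are shown:
- exact two-sided: p = 2 × 0.5^b
- uncorrected chi-square on 1 df: (b − c)²/(b + c) = b
- continuity-corrected chi-square on 1 df: (b − 1)²/b

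| b | exact | uncorrected | corrected |
|---|---|---|---|
| 3 | 0.25 | 0.083 | 0.248 |
| 4 | 0.125 | 0.0455 | 0.134 |
| 5 | 0.0625 | 0.025 | 0.074 |
| 6 | 0.031 | 0.014 | 0.041 |
| 8 | 0.008 | 0.005 | 0.013 |

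The threshold is four changers for the uncorrected form and six for the other two. The arm does not enter the calculation.

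**Participation period.** The run-in is 7 to 21 days (Protocol 2.5) and treatment is 24 weeks = 168 days. (7 + 168)/7 = 25 weeks and (21 + 168)/7 = 27 weeks from Visit 1. It can run longer, because Protocol 6 and 6.5 keep subjects on treatment until a delayed end-of-study CT is done. A subject who satisfies both exclusion 19 and the objective must have a date beyond that point.

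**Size of the denominator (assumed).** The documents give no share of subjects with a qualifying date. Across an assumed range of an arm of 111:

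| assumed share | subjects | exact test |
|---|---|---|
| 1% | 1 | cannot reach 0.05 |
| 2% | 2 | cannot reach 0.05 |
| 5% | 6 | needs all 6 to change |
| 10% | 11 | needs 6 of 11 |
| 20% | 22 | needs 6 of 22 |

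Suppose also that each such subject has a 30% chance of changing their mind, in any arm. The chance of exact p < 0.05 in that arm is then 0.001 with 6 subjects, 0.078 with 11 and 0.687 with 22. The result is driven by how many such subjects were enrolled and how often people change their minds.

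**The case against.** The strongest case against runs as follows.

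- **There is no outright contradiction.** Exclusion 19 concerns surgery within the study. The objective requires a date but not one inside the study, so a subject dated later satisfies both. *This stands.* A reader might infer that exclusion 19 leaves the endpoint with almost nobody. The documents do not show that: they give neither a count nor a distribution of dates. What they support is a restricted denominator of unknown size.
- **Exclusion 19 does not cause the one-way movement.** *This stands.* The cause is that everyone in the denominator is approved at entry. Deleting the exclusion would not change it.
- **The SAP governs the analysis and does not apply McNemar here.** *This stands in part.* Protocol 9 defers detail to the SAP, and the SAP's McNemar analyses concern items that can move both ways. A reader might infer that the final analysis will report a significant fall in surgery for this endpoint; SAP 7.6.1 does not provide for that. But the SAP's statement that it supersedes earlier text refers to the original protocol and an earlier SAP. For Amendment 6.0 it claims full agreement, and it keeps the endpoint. So Protocol 9.6 is neither implemented nor withdrawn.
- **Spurious significance and a tiny denominator cannot both bite.** *This stands.* They are alternatives: with one or two subjects the test is empty, and with many it is uninformative about drug.
- **The test could be run on the whole arm, where no-to-yes is possible.** That is a different endpoint from the stated percentage of approved subjects, and close to the willingness question already analysed.
- **Little depends on it.** *This stands.* The endpoint lies outside the Type I error hierarchy, and SAP 7.6.1 already compares two related items with placebo.

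**Conclusion.** The point holds in a limited form.

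- The McNemar test in Protocol 9.6 is wrong for the approved-for-surgery endpoint. With no possible movement in the other direction, exact p < 0.05 follows once six or more subjects in an arm change their minds (four or more for the uncorrected form). This applies to placebo as well, and nothing is compared with placebo.
- Separately, exclusion 19 confines the denominator to dates after participation ends, nominally 25 to 27 weeks from Visit 1 and later if the final CT is delayed. The documents neither state this nor size it.
- The SAP retains the objective and endpoint, supplies no analysis, and does not list the gap among its changes.

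The p-value thresholds are arithmetic and rest only on the denominator as defined in Protocol 2.3 and 7.3. The counts per arm are assumptions. The effect is confined to one other-secondary health-economic endpoint; primary, key secondary and safety conclusions do not change.

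**What to change.** 1. In Protocol 9.6, remove McNemar's test for the approved-for-surgery endpoint.
2. In SAP 7.6.1, define the denominator (who counts as approved with a date, from which recorded item, and what counts as no longer electing surgery). Report n/N by arm descriptively. Alternatively, drop the endpoint from Protocol 2.3, 3.2.1.3 and 7.3 and SAP 3.3.3 and 3.4.5, and record the removal in SAP Section 11.
3. For the comparative question, rely on the willingness-to-consider-surgery item, which SAP 7.6.1 already compares between arms by logistic regression with baseline response as a covariate.
4. The sponsor should reconcile Protocol 2.3 and 7.3 with exclusion 19 and state which scheduled dates are compatible with entry. The eligibility rule itself is the sponsor's to settle.

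The cost is wording in the protocol and SAP, with no new data and no change to sample size. One other-secondary endpoint loses its p-value.

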#### **4.3 Withdrawal and Removal of Subjects**

Subjects will be informed that they are free to withdraw from study treatment and/or the study at any time at their own request without prejudice to their future medical care, or that they may be withdrawn at any time at the discretion of the investigator or Sponsor for safety, nonadherence to protocol requirements, or administrative reasons (eg, termination of study by Sponsor). Subjects wishing to withdraw from study treatment will be strongly encouraged to continue in the study and have all scheduled study procedures performed.

A subject must be withdrawn from treatment for the following reasons:

- subject becomes pregnant
- A subject's study treatment will be discontinued if the investigator or Sponsor considers it in the subject's best interest to stop treatment, (eg, for safety or significant tolerability reasons such as an AE). Subjects who have one of the following AEs must be withdrawn from study treatment.
  - IOP of >21 mm Hg
  - nasal septal perforation
  - new onset or worsening of cataract

A subject may also be withdrawn from study treatment for the following reasons:

- lack of efficacy
- protocol violation

A subject may be withdrawn from the study for the following reasons:

- withdrawal of consent
- adverse event
- protocol violation that makes it unsafe for the subject to continue in the study
- termination of the study

- lost to follow up
- public health measure
- other

If a subject withdraws from the study after starting study treatment, appropriate follow-up must be conducted wherever possible.

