## 6.3 Visits 3, 4, and 5 (Weeks 4, 8, and 12)

During the 24-week double-blind treatment phase, subjects will return to the study site at Weeks 4, 8 and 12 to have efficacy and safety assessments performed.

At all visits during the double-blind treatment phase, treatment compliance will be monitored as described in [Section 5.7](#). Subjects will be given a double-blind study drug kit (containing 2 devices) assigned through the IWRS at Visit 3/Week 4 and Visit 4/Week 8. Subjects will receive 3 kits at Visit 5/Week 12. Subjects will be instructed to bring the study drug kits with them to each visit.

Subjects will be required to keep a daily diary of nasal symptoms through Week 12. The diary will be completed immediately before the morning and evening doses and will include recording of both instantaneous and reflective scores for nasal symptoms (see [Section 7.2](#)). Subjects will also be instructed that the use of rescue medication for CRS symptoms is not allowed until after

the Week 4 visit; starting at the Week 4 visit, they will be instructed to record use of the approved rescue medication in the electronic diary. Subjects will be instructed to bring the diary with them to all study visits.

The site staff will continue to monitor electronic diary transmission reports throughout the first 12 weeks of double-blind treatment to ensure that subjects are recording both morning and evening nasal symptoms and rescue medication use and that the data are being transmitted to the data base. Site staff should follow-up with subjects as necessary to counsel them on completion of the electronic diaries.

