#### **6.4 Subject Contact (Week 16 and Week 20)**

Subjects will be contacted at Weeks 16 and 20 (approximately every 4 weeks after Visit 5 (Week 12) and before Visit 6 (Week 24) to obtain information on treatment compliance, exacerbation assessment, AEs, and concomitant medications.

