#### **6.5 Visit 6 (Week 24 End-of-Double-blind/Early Termination)**

Subjects who complete the 24-week double-blind treatment phase, and those who prematurely withdraw from the study for any other reason during this phase should return to the study site and have the end-of-study/ET from study visit performed, including a CT scan. If a subject could not complete EOS CT scan at the Week 24 visit, subject should have all other scheduled procedures performed and continue on study treatment until an EOS CT scan can be completed. Additional Treatment kits can be dispensed via the 'Unscheduled Visit' functionality and the Visit 6 contact should not be completed in IWRS. If subject continues treatment, study staff will complete subject contacts approximately every 4 weeks to assess safety until subject can complete the EOS CT scan. When EOS CT scan has been completed and subject returns to study site, study staff will perform an additional SNOT-22, urine pregnancy test (women of child bearing potential only), and contact IWRS to complete Visit 6.

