### 7.4.3 Ocular examinations

An ocular examination must promptly be performed if a subject experiences any unexplained worsening in vision during the study (e.g. difficulty reading or seeing traffic signs from a

distance). The examiner must be a health care provider with expertise in examination and diagnosis of conditions of the eye. Reports will be forwarded to the investigator.

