## 8 SAFETY MONITORING AND REPORTING

### 8.1 Adverse Events

An AE is any untoward medical occurrence associated with the use of an investigational product in humans, whether or not considered related to the investigational product. This includes any occurrence that was new in onset or aggravated in severity or frequency from the baseline condition.

In this study, symptoms of CRS are collected as part of the primary and secondary endpoints. Changes or worsening of symptoms of CRS should not be reported as AEs. All events that meet the definition of a SAE will be reported as SAEs, regardless of whether they are protocol-specific assessments.

Abnormal results of diagnostic procedures, including laboratory test abnormalities, or from the nasal examination are considered AEs if they result in:

- discontinuation from the study treatment or discontinuation from the study
- require treatment or any other therapeutic intervention
- require further diagnostic evaluation which confirms a clinical significant abnormality (excluding a repetition of the same procedure that rules out an abnormality)
- are associated with clinical signs or symptoms that would have a significant clinical impact, as determined by the investigator

Subjects are encouraged to report AEs spontaneously or in response to general, non-directed questioning. All non-serious AEs are to be followed until the subject completes the study or is lost to follow-up.

Timely, accurate, and complete reporting and analysis of safety information from clinical studies is crucial for the protection of subjects, is the responsibility of the investigators and the Sponsor, and is mandated by regulatory agencies worldwide.

Each AE is to be documented on the CRF with reference to intensity, date of occurrence, duration, frequency, treatment, action taken regarding study drug, and outcome. Furthermore, each AE is to be classified as being serious or non-serious. Additionally, the investigator has to assess whether the AE is drug related (adverse drug reaction) or not. Changes of AEs and dates of ending have to be documented on the CRF.

Surgical procedures, planned before enrollment of the subject in the study, are not considered AEs if the condition(s) was (were) known before study inclusion. In the latter case, the medical condition should be reported in the subject's medical history.

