#### **SEPTAL EROSION/PERFORATION**

- Location
  - ◆ anterior, including the nasal valve area
  - ◆ posterior to nasal valve
  - ◆ both
- Severity
  - ◆ evidence of epithelial erosion
  - ◆ evidence of ulceration through the epithelial layer with exposed cartilage
  - ◆ perforation
    - diameter of perforation
- Is the septal erosion/perforation related to injury/trauma?

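### The one symptom that opens the protocol-required eye examination behind two compulsory treatment stops is never asked about directly during treatment; one question at existing contacts would fix this cheaply (minor).

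*Protocol*

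**What the plan says.** Protocol 4.3 makes three AEs compulsory reasons to stop study drug: "Subjects who have one of the following AEs must be withdrawn from study treatment". They are IOP above 21 mm Hg, nasal septal perforation, and new or worsening cataract. The same bullet also stops treatment whenever the investigator or sponsor judges this to be in the subject's best interest.

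Neither the protocol's Schedule of Study Procedures and Evaluations nor its copy in SAP Table 3.1 has an ocular row. Protocol 7.4.3 supplies the examination that replaced the scheduled ones: "An ocular examination must promptly be performed if a subject experiences any unexplained worsening in vision during the study". SAP 8.6 repeats this and places the results in listings.

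On how complaints are gathered, Protocol 8.1 says: "Subjects are encouraged to report AEs spontaneously or in response to general, non-directed questioning". The Week 16 and Week 20 contacts (6.4) are made "to obtain information on treatment compliance, exacerbation assessment, AEs, and concomitant medications". For drug supply over the second half of treatment, 6.3 says: "Subjects will receive 3 kits at Visit 5/Week 12". For subjects who stay on drug because the final CT is delayed, 6.5 says that "study staff will complete subject contacts approximately every 4 weeks to assess safety until subject can complete the EOS CT scan".

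At entry, exclusion 36 removes anyone reporting unexplained worsening of vision in the previous 3 months, and exclusions 26, 27 and 28 remove glaucoma or ocular hypertension, IOP elevation on steroids, and cataract (unless both natural lenses are gone).

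**The concern.** A compulsory stopping rule is only as good as the route by which its criteria come to light. For the two ocular criteria, the required route has a single gateway: the subject has to report that vision has worsened. The plan treats this symptom as important enough to ask about before randomization and to require a prompt examination after it, yet during treatment it leaves the symptom to spontaneous mention or an open question about health in general.

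A subject who puts gradual difficulty with reading down to age or tiredness may not volunteer it at a visit about sinus disease. That subject gets no triggered examination and may stay on a corticosteroid that 4.3 would require to be stopped. What is at stake is individual safety in a small number of subjects at most. Safety summaries are descriptive (Protocol 9.9), so no efficacy conclusion depends on this.

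**Working it through.** The plan states no figure to reproduce. The check sets the sections side by side and counts from the Schedule.

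**Step 1. What 4.3 needs and what measures it.** Two ocular criteria; scheduled IOP or lens assessments: 0. Eye examinations the protocol requires: 1, the symptom-triggered one in 7.4.3.

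**Step 2. How the trigger is elicited.** AE collection is marked at six on-treatment points. Section 8.1 governs all of them, and neither 6.3 to 6.5 nor the Schedule adds a vision item. Planned treatment is 24 × 7 = 168 days; days left = 168 − 7 × week.

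| Point | Type | AE collection | Directed vision question | Planned treatment days left |
|---|---|---|---|---|
| Week 4 | visit | yes | no | 168 − 28 = 140 |
| Week 8 | visit | yes | no | 168 − 56 = 112 |
| Week 12 | visit | yes | no | 168 − 84 = 84 |
| Week 16 | contact | yes | no | 168 − 112 = 56 |
| Week 20 | contact | yes | no | 168 − 140 = 28 |
| Week 24/ET | visit | yes | no | 168 − 168 = 0 |

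Result: AE collection at 6 of 6, a directed question at 0 of 6. At five of the six points a yes could still lead to withdrawal with planned treatment remaining. At Week 24 it serves detection and follow-up, unless drug continues for a delayed CT.

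**Step 3. The stretch without a clinic visit.** Week 12 to Week 24 is 168 − 84 = 84 of 168 planned days. With the ±7-day window at each end it is 84 − 14 = 70 to 84 + 14 = 98 days. Two subject contacts fall in it, so AE collection does continue.

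**Step 4. Who is exposed.** Planned on active drug: 2 × 111 = 222 of 333.

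**Step 5. The symptom at entry and on treatment.** Exclusion 36 and 7.4.3 describe the same symptom with the same examples. Eligibility is checked at Visits 1 and 2, before the first double-blind dose. The wording therefore exists and has been judged usable with subjects; it is simply not used again.

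**Step 6. What cannot be computed.** The documents give no frequency of IOP or lens events and no share of them with visual symptoms, so neither the number missed nor the gain from asking can be estimated.

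**The case against.** General, non-directed AE questioning is ordinary practice and was chosen for the whole study. Asking directly about one organ makes visual complaints solicited while all others stay unsolicited. That stands as a downside, though it applies equally in all arms and under the blind.

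Existing protection is considerable. The entry exclusions remove known ocular risk. Section 4.3 lets treatment stop in the subject's best interest without an IOP or lens reading, and 6.6 allows an unscheduled assessment at any time. This is why the point is minor.

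Timing also counts. SAP 4.5 records that both blinded interim analyses had been done, so a change at that stage would reach only subjects still being treated and would alter elicitation part-way through. Question counts based on all 333 subjects are upper limits.

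Three stronger readings are tempting and not supported:

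- *The 4.3 rule cannot operate, or dropping the scheduled examinations was a mistake.* Other routes exist, and the version history for Amendment 4.0 gives reasons: pandemic access and extensive earlier ocular safety data.
- *An acuity-only check would satisfy 7.4.3 and leave the criteria undecided, because IOP and lens status are not named.* The section requires that "The examiner must be a health care provider with expertise in examination and diagnosis of conditions of the eye". Someone so qualified, working up unexplained visual worsening, would be expected to assess both, and 6.6 covers an incomplete report. It is true that Attachment 3 itemizes septal findings down to the "diameter of perforation", but that summarizes a worksheet for a scheduled nasal examination done in every subject; less detail for an unscheduled specialist examination is to be expected.
- *Cases are being missed at some rate.* The documents give no basis for a rate.

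**Conclusion.** The point holds as a minor, cheap improvement. The required ocular safeguard depends on one symptom, and that symptom is sought by a directed question at none of the six on-treatment AE collection points, although the protocol already has the words for it. A question would strengthen the symptom route only; it would not restore the missing measurement, and symptomless rises in IOP or lens changes would remain undetected.

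The conclusion assumes that the protocol text reflects what sites ask. The consent pages, the CRFs and the COVID-19 guidance document mentioned in SAP 4.6.2.1 were not available. If the CRF or site guidance already carries a directed vision question at these contacts, the point is met.

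**What to change.** At Weeks 4, 8, 12, 16, 20 and 24/ET, and at each later contact for subjects kept on drug for a delayed CT, ask: *Since the last contact, have you had any unexplained worsening of vision, for example difficulty reading or seeing traffic signs from a distance?* A yes triggers the examination in 7.4.3.

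Matching edits: an exception to non-directed questioning in 8.1; the item added to 6.3, 6.4 and 6.5; a row in the protocol Schedule and in SAP Table 3.1. Sections 4.3 and SAP 8.6 can stay as they are, and no scheduled examination is added.

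Cost at full enrollment and attendance: 333 × 5 = 1,665 questions through Week 20, or 333 × 6 = 1,998 including Week 24, plus one per later contact. Expect slightly more visual complaints and triggered examinations. The study report should say that vision was solicited, and from what date if the change comes part-way through.

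Optional clarification only: a sentence in 7.4.3 naming IOP and lens status as items to record.
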